15.7.2 Incomplete Stop Date

The following rules will be applied to impute the missing numeric fields. If the date of the last dose of double-blind study treatment is missing, it will be replaced with the last visit date. If the imputed stop date is before the start date (imputed or non-imputed), then the imputed stop date will be equal to the start date.

Missing month and day

- If the year of the incomplete stop date is the same as the year of the date of the last dose of double-blind study treatment, then the month and day of the date of the last dose of study treatment will be assigned to the missing fields;
- If the year of the incomplete stop date is before the year of the date of the last dose of double-blind study treatment, then December 31 will be assigned to the missing fields;
- If the year of the incomplete stop date is after the year of the date of the last dose of double-blind study treatment, then January 1 will be assigned to the missing fields.

Missing month only

• If only the month of the incomplete stop date is missing, the day will also be treated as missing, and both month and day will be replaced according to the procedure described above.

Missing day only

• If the month and year of the incomplete stop date are the same as the month and year of the date of the last dose of double-blind study treatment, then the day of the date of the last dose will be assigned to the missing field;

Confidential Page 46 of 72

- If either the year of the incomplete stop date is before the year of the date of the last dose of double-blind study treatment or if the years are the same but the month of the incomplete stop date is before the month of the date of the last dose of double-blind study treatment, then the last day of the month will be assigned to the missing field;
- If either the year of the incomplete stop date is after the year of the date of the last dose of double-blind study treatment or if the years are the same but the month of the incomplete stop date is after the month of the date of the last dose of double-blind study treatment, then the first day of the month will be assigned to the missing field.

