7.7 Prior and Concomitant Medications

Use of all concomitant medications will be recorded in the patient's eCRF. Drug name and dates of administration must be recorded for all prescription drugs, herbal products, vitamins, minerals, and over-the-counter medications. Any changes in concomitant medications will also be recorded in the patient's eCRF. Any concomitant medication deemed necessary for the welfare of the patient during the study may be given at the discretion of the Investigator, eg, limited, acute prescribed opioid use. However, it is the responsibility of the Investigator to ensure that complete details regarding the medication are recorded in the eCRF.

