8.3 Prior and Concomitant Medication

The latest version of the *World Health Organization Drug Global* (WHODG) will be used to code prior, prior concomitant, and concomitant medications. *Prior medication* is defined as any medication started and stopped before the date of the first dose of double-blind study treatment. A *prior concomitant medication* is any medication that started before the date of the first dose of double-blind study treatment and stopped or is ongoing after the date of the first dose of study treatment. *Concomitant medication* is defined as any medication taken on or after the date of the first dose of double-blind study treatment. Both prior and concomitant medications, including prior concomitant medication use, will be summarized as the number and proportion of patients in each treatment group who received each medication within each therapeutic class (ie, Anatomical Therapeutic Chemical code, Levels 2, 3 and 4) and preferred term for the Safety Population. Multiple medications used by a patient will only be counted once.

Any concomitant medication started after the date of the last dose of double-blind study treatment will not be included in the summary but will be included in the patient data listings.

Confidential Page 19 of 72

9. EFFICACY ANALYSES

The primary efficacy analyses and will be based on the mITT Populations, respectively; other efficacy analyses will be based on the ITT Population, unless stated otherwise. The baseline for each specific efficacy endpoint is defined as the last measurement prior to the first dose of randomized treatment. All statistical hypothesis tests will be performed at the 2-sided 5% significance level for main effects. All confidence intervals (CIs) will be 2-sided 95% CIs, unless stated otherwise.

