15.7 Missing Date Information for Prior or Concomitant Medications

For prior or concomitant medications, including psychotropic medications, incomplete (ie, partially missing) start dates and/or stop dates will be imputed. If the start date and the stop date for a patient are both incomplete, the start date will be imputed first.

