15.7.1 Incomplete Start Date

The following rules will be applied to impute the missing numeric fields. If the stop date is complete and the imputed start date is after the stop date, then the start date will be imputed using the stop date.

Missing month and day

- If the year of the incomplete start date is the same as the year of the date of the first dose of double-blind study treatment, then the month and day of the date of the first dose of double-blind study treatment will be assigned to the missing fields;
- If the year of the incomplete start date is before the year of the date of the first dose of double-blind study treatment, then December 31 will be assigned to the missing fields;
- If the year of the incomplete start date is after the year of the date of the first dose of double-blind study treatment, then January 1 will be assigned to the missing fields.

Confidential Page 45 of 72

Missing month only

• If only the month of the incomplete start date is missing, the day will also be treated as missing, and both month and day will be replaced according to the procedure described above.

Missing day only

- If the month and year of the incomplete start date are the same as the month and year of the date of the first dose of double-blind study treatment, then the day of the date of the first dose of study treatment will be assigned to the missing field;
- If either the year of the incomplete start date is before the year of the date of the first dose of double-blind study treatment or if the years are the same but the month of the incomplete start date is before the month of the date of the first dose of double-blind study treatment, then the last day of the month will be assigned to the missing field;
- If either the year of the incomplete start date is after the year of the date of the first dose of double-blind study treatment or if the years are the same but the month of the incomplete start date is after the month of the date of the first dose of double-blind study treatment, then the first day of the month will be assigned to the missing field.

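### SAP 15.7.1 and 15.7.2 re-date to Day 1, and count as concomitant, a drug with a year-only start in the first-dose year and a recorded stop month before first dose

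*SAP*

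**What the plan says.** SAP 15.7 covers prior and concomitant medications, psychotropic drugs included, and sets the order: "If the start date and the stop date for a patient are both incomplete, the start date will be imputed first".

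SAP 15.7.1 deals with the start. If only the year is known and it is the year of first dose, "then the month and day of the date of the first dose of double-blind study treatment will be assigned to the missing fields". For an earlier year, 31 December of that year is used. One check follows. It begins "If the stop date is complete and the imputed start date is after the stop date", and it then replaces the start by the stop. Nothing is said about a stop that is only partly known.

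SAP 15.7.2 deals with the stop and opens with "The following rules will be applied to impute the missing numeric fields". A stop with known month and year but no day, in a month before the last-dose month, goes to the last day of the recorded month. The section then adds an override that applies when "the imputed stop date is before the start date (imputed or non-imputed), then the imputed stop date will be equal to the start date".

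SAP 8.3 sorts the resulting dates. Prior medication "is defined as any medication started and stopped before the date of the first dose of double-blind study treatment". Concomitant medication "is defined as any medication taken on or after the date of the first dose of double-blind study treatment". Both are tabulated by treatment group for the Safety Population.

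**The concern.** The two checks do not protect the same information. The check in 15.7.1 respects a stop date only when the day is known. The override in 15.7.2 lets the start win even when that start was itself imputed. When the start is year-only and the stop has a month and year, the imputed start therefore displaces a stop month that the site actually recorded.

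Counting a drug as concomitant is a reasonable default when the known parts of its dates leave that open. Here they rule it out. The record is also treated less well than one with a complete stop date, although both show that the drug ended before first dose.

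What is at stake is the content of the SAP 8.3 tables: a drug that had ended is counted as concomitant. Because its imputed start is Day 1, it is not even classed as prior concomitant; it looks newly started.

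**Working it through.** The plan states no figure for this, so the check consists of following the rules on a case. The calendar dates are assumptions: first dose 10 Oct 2022 and last dose 20 Nov 2022 (first dose + 41 days). The recorded start is 2022 and the recorded stop is March 2022.

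1. **Start (15.7.1).** Start year 2022 = first-dose year, so start = 10 Oct 2022.
2. **Check on the start (15.7.1).** It needs a complete stop. The day is missing, so it is not applied.
3. **Stop (15.7.2).** Same year as last dose, and March is before November, so stop = 31 Mar 2022.
4. **Override (15.7.2).** 31 Mar is before 10 Oct, so stop = start = 10 Oct 2022.
5. **Class (8.3).** The drug did not start and stop before 10 Oct, so it is not prior. Its start is not before first dose, so it is not prior concomitant. It is concomitant.

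Neighbouring cases, with the same first and last dose:

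| Recorded start | Recorded stop | Dates after imputation | Class |
|---|---|---|---|
| 2022 | March 2022 | 10 Oct 2022 to 10 Oct 2022 | concomitant (wrong) |
| 2022 | 15 Mar 2022 | 15 Mar 2022 to 15 Mar 2022 | prior |
| 2022 | October 2022 | 10 Oct 2022 to 31 Oct 2022 | concomitant (possible on the record) |
| 2021 | March 2022 | 31 Dec 2021 to 31 Mar 2022 | prior |
| 2021 | March 2021 | 31 Dec 2021 to 31 Dec 2021 | prior |

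The last row shows that the override can also displace a recorded stop month when both dates lie in the year before first dose. The class is then unaffected.

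**Does the result depend on the example?** Take every day of 2022 as first dose, with a start recorded as 2022 and every stop month of 2022. The number of pairs with the stop month before the first-dose month is the sum over months of (days in month) × (month number − 1):

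0 + 28 + 62 + 90 + 124 + 150 + 186 + 217 + 240 + 279 + 300 + 341 = 2017

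All 2017 end as Day 1 to Day 1, concomitant. The January term is 0, so a first dose in January is never affected. The remaining pairs number 365 × 12 − 2017 = 2363. If the imputed start is capped at the imputed stop, all 2017 become prior with the recorded month kept, and 0 of the 2363 change.

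For year-only starts in the year before first dose, a run over first-dose dates from 1 Sep 2021 to 31 Dec 2023 (an assumed range) misclassified 0 of 15,418 combinations.

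These are counts of date combinations under a deterministic rule. They show where the rule applies, not how many patients it reaches.

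**The case against.** The strongest reply is that the case is narrow and the consequence slight. Several things must coincide: start month unknown, start year equal to first-dose year, stop month known, stop day unknown, and stop month before the first-dose month. The protocol limits how often this can happen: its section 7.7 states "Drug name and dates of administration must be recorded for all prescription drugs", and section 10.3.2 provides for completeness checks and queries. The only visible use of these dates is descriptive, and the rules make no reference to treatment arm. All of this stands, and it is why the point is minor. It does not make the classification right.

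A second reply is that 15.7.2 does not contradict itself. Its opening sentence limits it to missing fields, but the override is an explicit, specific rule that names the imputed-start case. That also stands. The fault lies in the result, not in a conflict with the stated scope.

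A reader might infer more in two directions. One is that any year-only start with a pre-dose stop month is misclassified. It is not: an earlier start year gives 31 December, and the drug stays prior.

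The other is that the primary analysis is affected, because a finished antidepressant would seem to start on Day 1 and the patient's later MADRS and CGI-S scores would be set to missing under SAP 9.1.1 and 9.2.1. The documents do not support that. The intercurrent-event tables cannot be read in the public text, and nothing visible says that dates imputed under 15.7 define new antidepressant therapy. Protocol 7.8 also requires patients who start a new treatment during the study to be discontinued, so a real new start should appear in the disposition data as well.

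**Conclusion.** Wrong as written, at minor severity. For a year-only start in the first-dose year, and a stop with known month and year but no day in a month before the first-dose month, the rules always give Day 1 to Day 1 and the class concomitant. The recorded stop month shows that class to be false. The effect that can be shown is confined to the prior and concomitant medication tables of SAP 8.3. The number of affected records cannot be derived from the documents and is probably small.

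The conclusion rests on a literal reading of 15.7 to 15.7.2 and 8.3. The calendar dates are illustrative; the result needs only the stated order of the months.

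**What to change.** Change both sections, because a change to 15.7.1 alone would leave the override in place.

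1. **15.7.1.** Extend the check on the start to a stop that is complete or has a known month and year. If the imputed start is later than that stop (as recorded, or as first filled in under 15.7.2), set the start to the stop. The program must therefore form the provisional stop before it applies the check.
2. **15.7.2.** Let the override move the imputed stop to the start only if the start date is complete, or if the result keeps the recorded month and year of the stop. A complete recorded start that falls after the recorded stop month is a contradiction in the data and should go to query. The same should hold for a start whose recorded month is after the recorded stop month.

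The example then becomes 31 Mar 2022 to 31 Mar 2022, prior, in line with what the SAP already does for a complete stop of 15 Mar 2022.

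The cost is two sentences and one program condition. For year-only starts in the first-dose year, no combination with a stop in the first-dose month or later changed in the enumeration (0 of 2363). Other forms of partial start were not enumerated and should be covered in program testing.

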15.8 Character Values of Clinical Laboratory Parameters

If the reported value of a clinical laboratory parameter cannot be used in a statistical summary table because, for example, a character string is reported for a parameter of the numeric type, the coded value will need to be appropriately determined for use in the statistical analysis. However, the actual values as reported in the database will be presented in the data listings.

Table 15-6: Example for Coding of Special Character Values for Clinical Laboratory Parameters

Laboratory Test	Possible Laboratory Results, SI Units	Coded Value for Analysis
Chemistry: ALT	< 5	5
Chemistry: AST	< 5	5
Chemistry: bilirubin, total	< 2	2
TIdeal deal done	$= OR > 8.0, \ge 8.0, > 0$	Positive
Urinalysis: ketones	≤0, negative	Negative
IIdad da al	> 8.0, ≥ 8.0	8.0
Urinalysis: pH	≥ 8.5	8.5
	≤ 50	0
	(50, 100]	1+
I Inimalantian almana	(100, 250]	2+
Urinalysis: glucose	(250, 500]	3+
	(500, 1000]	4+
	> 1000	5+
	≤0	Negative
	(0, 15]	0
I Inimalanian mantain	(15,30]	1+
Urinalysis: protein	(30,100]	2+
	(100,500]	3+
	> 500	4+

ALT = alanine aminotransferase; AST = aspartate aminotransferase; SI = Le Système International d'Unités (International System of Units).

Confidential Page 47 of 72

16.	I
	1

Confidential Page 48 of 72

  		
ļ		

Confidential Page 49 of 72

Intra-Cellular Therapies,	Inc.
Study ITI-007-502	

Statistical Analysis Plan Amendment 1

Confidential Page 50 of 72

